5. TRIAL PARTICIPANT DISPOSITION

5.1. DISPOSITION OF PARTICIPANTS

Relevant to the analyses described in this SAP, a CONSORT flow diagram will be constructed to describe how all of the participants who entered the study are accounted for including the following measures, as applicable:

The numbers of participants screened, screened out (with reasons for exclusion), enrolled, randomized, allocated to each study arm, received assigned intervention (with reasons for not receiving assigned intervention), reasons for discontinuation from follow-up (e.g., lost to follow-up, adverse event, noncompliance, etc.), and the number of participants with available data for each assay.

5.2. TREATMENT EXPOSURE

Self-reported pill taking will be reported by prescribed dosing day stratified by arm and overall. The summary measures will be number of doses reported taken and number of doses reported taken divided by number prescribed. The number and proportion of adherent participants will be reported by day and overall time.

6. BASELINE DATA

Baseline variables will include age, sex at birth, race, number of people in household, number of people in household enrolled in the study as contacts, number of infected contacts, underlying medical conditions (see below), contact type (HCW or household), household type, presence and number of children, number of bedrooms, number of bathrooms, number of days since contact with index case, duration of exposure to index case, current smoker, quarantine status hours of contact with the index case and the impact of pandemic on the participant's ability to work.

The following list of variables will be included and condensed into the following categories: metabolic disease (hypertension, diabetes mellitus type 1 and 2, and cardiovascular disease including atherosclerosis), non-communicable diseases (NCDs) (chronic cardiac disease excluding hypertension, chronic kidney disease, liver disease, chronic neurological disorder, chronic hematologic disease, rheumatologic disorder, dementia, malnutrition) infectious diseases not HIV, immunosuppressive disease (HIV, autoimmune disease and malignancy), lung disease (COPD, asthma) and other:

Chronic cardiac disease, including congenital heart disease and heart failure (not hypertension)

Hypertension

Diabetes mellitus: Type 1

Diabetes mellitus: Type 2

Chronic pulmonary disease, including COPD

Asthma (physician diagnosed)

Chronic kidney disease

Confidential

All proprietary rights reserved

Page 5 of 12

Moderate or severe liver disease

Mild liver disease

Chronic neurological disorder

Malignant neoplasm

Chronic hematologic disease

HIV

Rheumatologic disorder

Dementia

Malnutrition

Autoimmune disease

7. EFFICACY/EFFECTIVENESS ANALYSES

7.1. EFFICACY ANALYSES

Final (as opposed to interim) efficacy analyses will be stratified (baseline hazard) for enrollment site and contact type and adjusted by baseline variables as noted in each section below.

7.1.1. Primary efficacy analyses

Objective: To estimate the efficacy of HCQ (400 mg orally daily for 3 days then 200 mg orally daily for an additional 11 days, to complete 14 days) to prevent incident SARS-CoV-2 infection, compared to ascorbic acid among contacts of persons with SARS-CoV-2 infection.

Outcome: Polymerase chain reaction (PCR)-confirmed SARS-CoV-2 infection through Day 14

Cohorts: mITT Cohort, Sensitivity Cohort

Definition of Endpoint: An endpoint defining PCR test is defined as one with either concordant results or $Ct \leq 40$ and will be referred to as positive test for this analysis. PCR tests not meeting these criteria will be referred to as negative. A participant will be defined as having reached the endpoint on the midpoint between the days of collection of their first positive result and last negative result (prior to the positive result) in the first 13 days of follow-up. Participants who have confirmed COVID-19 through external evaluation in the first 13 days (e.g. hospital or clinical assessment) will be defined as having reached the endpoint at the midpoint between the last prior negative test and the day of the external diagnosis. Participants who do not reach the endpoint will have their follow-up censored at their last negative RNA test. Any uncertainty in final endpoint determination will be resolved by the blinded Endpoint Adjudication Committee.

Analysis Details:

The primary analysis will be performed on the mITT Cohort. A sensitivity analysis will be performed on the Sensitivity Cohort to account for potential missed infections at day 1.

We will use a Cox Proportional Hazards model with robust standard errors to estimate the hazard ratio and corresponding 95% confidence interval and Wald test statistic. Efficacy will be calculated as 1 minus the hazard ratio (treatment/control) from the treatment coefficient. Robust confidence intervals and p-values will be displayed. Per FDA guidance on prevention studies, the following variables will be included to increase precision: quarantine status, sex, and age of contact.

The number of evaluable participants per arm will be displayed (defined as participants with at least one PCR test result or external diagnosis) by arm with person-days of follow-up and number of endpoints per arm and prevalence of endpoints (number reached endpoint/number evaluable) with a 95% confidence interval calculated using exact binomial confidence intervals.

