9.1.4. Exit Contact (Day 28±3)

The Exit Contact will be conducted through Telehealth, online, by telephone, or by text messaging.

Exit Contact evaluations are as follows:

- Collect mid-nasal swab for PCR
- Review AEs
- Complete Exit Contact Survey (online, Telehealth, telephone, or text messaging). This Survey will include concomitant medication review and symptoms review.
- The Exit Contact Survey will include evaluation for SARS-CoV-2 infection and/or COVID-19 and associated testing and medical care.

- *If in DBS Sub-study, collect DBS samples for analysis of anti-SARS-CoV-2 antibodies (if possible).*

Clinical outcomes will be confirmed through the electronic health record, if possible.

The final swab will be collected by the courier or returned via the postal service.

9.1.5. *Participants who Develop COVID-19 During the Study*

Participants who develop symptoms concerning for COVID-19 will be instructed to contact their provider for clinical care and testing. Study results will be available to participants after study completion as they are not tested in real-time for clinical diagnosis.

Participants who develop SARS-CoV-2 infection may be sent a home pulse oximeter to measure the oxygen saturation to provide direct information for clinical assessment.

Participants with a clinical diagnosis of COVID-19 should continue on study therapy unless they are started on COVID-19 treatment outside this study. Other study procedures will continue, with early exit possible to document COVID-19 diagnosis.

9.2. *Index Cases*

9.2.1. *Baseline Evaluation: Day 1*

Participants will be assessed for study eligibility through a screening conducted through a web-based screening tool, Telehealth, telephone, or text messaging.

Day 1 evaluations are as follows:

- *Informed consent*
- *Collection of demographic information*
- *Check of inclusion and exclusion criteria*

Eligible participants will receive a swab kit either via courier or mail, which includes a Quick Start Instruction Card, a swab, a plastic tube for swab collection, and a return container with affixed Category B UN3373 label, as required by International Air Transport Association (IATA) guidelines [36].

The participant will do the following on Day 1:

- *Collect mid-nasal swab for PCR*
- *Complete Survey (online, Telehealth, telephone, or text messaging). This Survey will include assessment of risk for COVID-19 acquisition, engagement with testing and treatment, and symptom review.*

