11.3.1. Efficacy Analyses

Demographic characteristics (age, sex, race) of each study group will be tabulated.

The mean age (plus range and standard deviation) by sex of the enrolled participants, as a whole and per group, will be calculated.

The primary analysis will be performed using the modified Intention-to-Treat population. If the participant is not SARS-CoV-2 positive by laboratory test, their infection time will be censored at the last negative swab test date at or before the Day 14 swab. A logistic model stratified by site and accounting for within-household correlation will be used to assess the efficacy of the HCQ group compared to control. To aid understanding of the results from the logistic model, cumulative incidence Kaplan-Meier curves of time to infection will be presented by site and treatment arm.

Subgroup Analyses

All subgroup analyses will be pre-specified in the Statistical Analysis Plan. Any further subgroups will be considered *ad hoc*.

Missing Data

Due to the design of the study and retention activities, we expect to be able to categorize all infections as either incident or prevalent at baseline. However, in the unlikely event of a missing test result, the missing data will be imputed.

Additional analyses will be described in the Statistical Analysis Plan finalized before database lock.

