2.1. GENERAL DESIGN CONSIDERATIONS

Evaluations include safety and tolerability, SARS-CoV-2 detection, SARS-CoV-2 viral shedding, and coronavirus disease (COVID-19) diagnosis. Two study groups (one active and one receiving ascorbic acid [vitamin C], to serve as a placebo-equivalent comparator) will be enrolled to assess a daily dosing regimen administered for 14 days, which appears to be the upper limit of the incubation period of SARS-CoV-2 infection.

Up to 2000 eligible participants 18 to 80 years of age will be randomized (at the level of household) 1:1 to receive one of the following therapies:

- HCQ 400 mg orally daily for 3 days then 200 mg orally daily for an additional 11 days
- Ascorbic acid 500 mg orally daily for 3 days then 250 mg orally daily for 11 days

HCQ and ascorbic acid will appear similar, and taste will be partially masked as HCQ can be bitter and ascorbic acid will be sour.

During the study participants will perform the following:

- Collect mid-nasal swabs for viral detection for the primary trial endpoint
- Complete Surveys that will include questions about symptoms from both the drug regimen and virus infection, review of concomitant medications, and other pertinent topics

Note: Participants who report respiratory or other febrile illness will be referred for assessment to their primary care provider.

During the first 14 study days, participants take medication, complete Surveys, and collect mid-nasal swab to assess symptoms and virus exposure. On Day 28, a final swab is collected and Survey completed. The duration of study participation will be approximately 28 days.

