7.1.2. Secondary efficacy analyses

Infection by day 28

Objective: To test the efficacy of HCQ (400 mg orally daily for 3 days then 200 mg orally daily for an additional 11 days, to complete 14 days) to prevent incident SARS-CoV-2 infection two weeks after completing therapy, compared to ascorbic acid among contacts of persons with SARS-CoV-2 infection.

Outcome: Polymerase chain reaction (PCR)-confirmed SARS-CoV-2 infection through Day 28

Cohorts: mITT Cohort, Sensitivity Cohorts

Definition of Endpoint: An endpoint defining PCR test is defined as one with either concordant results or $Ct \leq 40$ and will be referred to as positive test for this analysis. PCR tests not meeting these criteria will be referred to as negative. A participant will be defined as having reached the endpoint on the midpoint between the days of collection of their first positive and last negative PCR tests (prior to a positive test). Participants who have confirmed COVID-19 through external evaluation (e.g. hospital or clinical assessment) will be defined as having reached the endpoint at the midpoint between the last negative test (prior to external diagnosis) and the day of the external diagnosis. Participants who do not reach the endpoint will have their follow-up censored at their last negative test. Any uncertainty in final endpoint determination will be resolved by the blinded Endpoint Adjudication Committee.

Analysis Details: The same analytical approaches will be applied as for the primary efficacy analysis, including a primary analysis on the mITT Cohort and a sensitivity analysis on the Sensitivity Cohort.

Duration of shedding

Objective: To test the efficacy of HCQ to shorten the duration of SARS-CoV-2 shedding among those with SARS-CoV-2 infection.

Outcome: SARS-CoV-2 viral shedding by PCR

Cohort(s): mITT Cohort

Definition of Endpoint: For this analysis, a positive PCR test is defined as one where both targets are identified or one target is identified with $Ct \leq 40$.

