PCR tests not meeting these criteria will be referred to as negative. The endpoint will be defined as the number of days from the first positive test until virus is no longer detected (a negative test has been observed with no positive tests following). Censoring will be indicated if the participant is still shedding on day 14. Participants who have a COVID-19 related hospitalization or death will be assumed to shed through day 14 and would have their days of shedding censored as if they had been observed through day 14.

Analysis Details: We will use a Cox Proportional Hazards model with robust standard errors to estimate the hazard ratio and corresponding 95% confidence interval and Wald test statistic. Robust confidence intervals and p-values will be displayed. This analysis represents a subset selected post-randomization and therefore requires adjustment for confounders. Due to lack of known confounders early in the epidemic, we propose that the list of baseline descriptors be assessed individually for their association with the primary endpoint. Those associated univariably with $p < 0.10$ will be included in this analysis. A hazard ratio greater than 1 (treatment/control) indicates efficacy of the intervention in shortening shedding.

Prevention of COVID-19 diagnosis

Objective: To test the efficacy of HCQ to prevent incident COVID-19.

Outcome: PCR-confirmed COVID-19 diagnosis post start of HCQ therapy through Day 14

Cohort(s): ITT, mITT, Sensitivity, Seronegative, Infected

Definition of Endpoint: COVID-19 is defined as symptomatic disease based on the following criteria with virologic confirmation (RNA PCR Ct \leq 40):

- At least TWO of the following symptoms: Fever ($\geq 38^{\circ}\text{C}$), chills, rigors, myalgia, headache, sore throat, new olfactory and taste disorder(s), OR
- At least ONE of the following symptoms: cough, shortness of breath or difficulty breathing, OR
- Severe respiratory illness with at least 1 of the following:
 - Clinical or radiological evidence of pneumonia, OR
 - Acute respiratory distress syndrome (ARDS)

A participant will be defined as having reached the endpoint if they have the diagnosis above. The time of the endpoint will be the onset of symptoms. Participants who do not have the endpoint will be censored at the last time they were known to be symptom-free. Death and hospitalization will be counted in the endpoint.

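### SAP 7.1.1 censors contacts without a primary event at their last negative test with no Day 14 limit, so the Day 28 swab can set time at risk inside the Day 14 analysis

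*SAP*

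**What the plan says.** SAP 7.1.1 sets the horizon in its outcome line: "Outcome: Polymerase chain reaction (PCR)-confirmed SARS-CoV-2 infection through Day 14". An event is dated at the midpoint of the "first positive result and last negative result (prior to the positive result) in the first 13 days of follow-up". External COVID-19 diagnoses count only within the same 13 days. For contacts without an event, the rule is "Participants who do not reach the endpoint will have their follow-up censored at their last negative RNA test". No upper day is given.

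Protocol 11.3.1 does give one: for a participant who is not positive, "their infection time will be censored at the last negative swab test date at or before the Day 14 swab".

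A swab after Day 14 is scheduled for every contact. SAP 2.1 states: "On Day 28, a final swab is collected and Survey completed". Protocol 9.1.4 allows three days either side.

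Two other SAP rules help in reading the primary one. The Day 28 secondary analysis in 7.1.2 uses almost the same sentence, "Participants who do not reach the endpoint will have their follow-up censored at their last negative test", and there it has to include the Day 28 swab. The shedding endpoint, also in 7.1.2, does name its limit: "Censoring will be indicated if the participant is still shedding on day 14". No other SAP text restores a Day 14 limit for the primary analysis.

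SAP 7.1.1 estimates a Cox hazard ratio and also displays person-days of follow-up by arm beside the endpoint counts.

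**The concern.** Events and censoring run on different clocks. Events stop at Day 14, while the test that ends follow-up for a non-event may be the Day 28 swab. For a contact swabbed daily through Day 14, this only lengthens follow-up past the last possible event. For a contact who stopped swabbing early, a negative result two weeks after the window fills in unobserved days inside it. An infection caught and cleared in that gap is then analysed as observed event-free time.

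Three things are at stake: the displayed person-days, the 14-day cumulative incidence (also requested by subgroup in SAP 7.1.4), and the hazard ratio if one arm stops swabbing more than the other. The interim monitoring in SAP 8.1 uses the same primary outcome.

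**Working it through.** **The plan's own figures.** SAP 2.4 assumes 10% risk in control, a 50% reduction and 93 events: 93 / ((0.10 + 0.05)/2) = 1240, or 620 per arm at 1:1. Integrating the SAP 8.1 bounds at 19, 37, 56, 74 and 93 events gives one-sided alpha 0.0250 (futility binding) and power 90.2% at a hazard ratio of 0.5. So the design reproduces, and none of these figures depends on the censoring rule.

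**One contact under both rules.** Put Day 1 at time 0, so Day 14 is time 13 and Day 28 is time 27. The last daily swab is negative on Day 5 (time 4).

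| Day 28 swab | SAP 7.1.1 as written | Limited to Day 14 |
|---|---|---|
| Negative | censored at time 27; at risk through Day 14 | censored at time 4 |
| Positive | midpoint (4 + 27)/2 = 15.5, outside 13 days; censored at time 4 | censored at time 4 |
| Missing | censored at time 4 | censored at time 4 |

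All three are non-events under either rule; only time at risk differs. One exception depends on the reading. If the 13-day limit applies to the midpoint, a contact last negative on Day 1 to 3 with a positive exit swab on Day 25 has a midpoint between (0 + 24)/2 = 12 and (2 + 24)/2 = 13, and would be a primary event.

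Cutting the time axis at Day 14 does not cure this. The contact in the top row would still be in every risk set up to Day 14. The limit has to apply to which tests may set the censoring date.

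**Person-days.** Inputs: 620 control contacts and 10% risk (SAP 2.4), so 62 events and 558 non-events. Assumptions: event times uniform over 13 days (mean 6.5), complete swabbing, and all non-events negative at Day 28.
- Limited to Day 14: 558 × 13 + 62 × 6.5 = 7,657.
- As written: 558 × 27 + 62 × 6.5 = 15,469.

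**Hazard ratio with no true effect.** The documents give no rate of early stopping. Assumptions: constant hazard giving 10% over 13 days, stoppers quit after Day 5, 20% of missed infections still positive at Day 28, and no external diagnoses in the gap. Being free of infection at Day 5 has probability 0.9^(4/13) = 0.968, so the risk from Day 5 to Day 14 is 0.968 − 0.900 = 0.068.

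With full Day 28 return, the risk sets of the two arms stay almost equal, so the hazard ratio is close to the ratio of observed events, (0.100 − 0.068 × s_HCQ) / (0.100 − 0.068 × s_control), where s is the share stopping early:
- 10% against 5%: 0.0932/0.0966 = 0.965
- 20% against 10%: 0.0864/0.0932 = 0.927
- 30% against 10%: 0.0796/0.0932 = 0.854

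Solving the Cox score equation on expected daily counts gives:

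| HCQ vs control stopping | Full Day 28 return | 50% return | Same Cox model, Day 14 limit |
|---|---|---|---|
| 10% vs 5% | 0.96 | 0.98 | 1.00 |
| 20% vs 10% | 0.93 | 0.96 | 1.00 |
| 30% vs 10% | 0.85 | 0.92 | 1.00 |
| 20% vs 20% | 1.00 | 1.00 | 1.00 |

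A separate simulation of 400,000 contacts made other assumptions (stopping day uniform over Days 1 to 13, 90% return, mean shedding 14 days). For 30% HCQ against 10% control it gave 0.88 as written and 0.98 with the limit.

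**Cumulative incidence when stopping is equal.** In the same kind of simulation, with mean shedding of 10 to 20 days, the hazard ratio did not move. The control Kaplan-Meier estimate at Day 14 (true value about 10%) fell to 9.5–9.6% with 10% stopping and 9.1–9.2% with 20%. It stayed at about 10.0% with the limit.

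**The case against.** The best case against the point is that this is loose drafting. The outcome line and the event rule in the same SAP paragraph both set a Day 14 horizon, so a programmer may well read the censoring sentence inside it. That is fair as to intent: a reader might infer that the SAP deliberately withdrew the protocol's limit, and nothing in it says so. But the sentence as written has no limit, and cutting the time axis at Day 14, the natural charitable reading, leaves the risk-set problem in place.

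A reader might also infer that the SAP spoils a protocol analysis that would have been unbiased. The documents do not support this. The protocol's primary model is logistic. If early stoppers without a positive swab are scored as non-events, it gives odds ratios of 0.96, 0.92 and 0.84 in the three unequal scenarios, unless the imputation mentioned in Protocol 11.3.1, which is not specified there, corrects them. The value of 1.00 belongs to the SAP's Cox model with a Day 14 limit.

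Several facts limit the likely size. Protocol 11.3.1 calls a missing result unlikely, and 6.4 cites annual site retention above 80% to 90%. Contacts who stop treatment stay on study with all evaluations (7.4, 8.1), so drug intolerance is not planned to end swabbing. External diagnoses within 13 days count as events, and the exit survey asks about infection; the calculations omit both and so may overstate missed infections. Full Day 28 return among people who quit daily swabs is generous, which is why the 50% column is shown.

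On person-days, the SAP plans no rate per person-day. Its stated measure is endpoints over evaluable participants, which censoring does not touch. A halved infection rate is therefore something a reader might calculate from the display, not a planned result.

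**Conclusion.** The point holds as a flaw in a stated rule, of modest and conditional size. As written, a swab taken after the primary window sets time at risk inside it for contacts who stopped daily swabs early, and days without any test count as event-free.

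- **Certain, even with perfect adherence:** displayed person-days include Days 15 to 28 and about double (15,469 against 7,657 in control, with full Day 28 return).
- **Conditional on early stopping:** Day 14 cumulative incidence is understated, by about 0.5 percentage points at 10% stopping under the simulation's assumptions.
- **Conditional on stopping that differs by arm:** under no true effect the hazard ratio is 0.85 to 0.98 across the scenarios, in favour of whichever arm stops more. With equal stopping there is no shift, and contacts swabbed through Day 14 never affect the Cox estimate.

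Two stronger readings should be resisted. One is that the Day 28 result decides whether a contact counts as an event; apart from the narrow exit-window case, it changes time at risk only. The other is that the trial's hazard ratio is biased toward HCQ; that needs unequal stopping, for which the documents give no figure.

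**What to change.** In SAP 7.1.1, have contacts without an event *censored at the last negative RNA test collected on or before Day 14*, and count person-days only to that date. Apply the same limit to the Day 14 infection analyses in 7.1.3 and 7.1.4, which take over the primary approach. Keep the rule without a limit only for the Day 28 analysis in 7.1.2.

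The cost is one clause and one line of code, with no new data. The drawback is slightly less risk time for contacts who skipped the late daily swabs but returned one at Day 28. The event target and sample size do not change.

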2.3. RANDOMIZATION

Enrolled contacts were randomized 1:1 to receive either HCQ or ascorbic acid. Randomization tables were stratified by study site and contact type (household/social exposure or healthcare worker exposure) and blocked into groups of randomly varying size. The tables were programmed in R and allocation was performed via REDCap by site pharmacists or their designees. All other study staff were blinded to randomization group apart from the coordinating center's unblinded statistical team.

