2.4. SAMPLE SIZE AND POWER

Since finalization of the protocol and at the recommendation of the DSMB, the study size has been recalculated as an event-driven design. The original study was designed under 80% power with a target number of households, assuming 1 infection per household, recognizing there would

likely be more than 1 per household and therefore power would be at least 80%. In the spirit of accounting for the within household correlation without any existing estimates of what it may be, we instead assume 90% power with 50% reduction and 4 interim analyses (for 5 total) and a one-sided alpha = 0.025 and a hard futility boundary. Under these design assumptions, the design requires 93 events. Assuming a household attack rate of 10% in the placebo arm (higher than in protocol and based on emerging evidence (UM study and HH study from China that looked at masks and disinfecting), we would need to enroll 1240 participants who are negative at baseline.

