8.1. EFFICACY AND FUTILITY MONITORING

Interim monitoring will be performed on the primary outcome after approximately 20%, 40%, 60% and 80% of expected events. Monitoring will be performed using asymmetric O'Brien-Fleming bounds for early stopping for efficacy (lower) and futility (upper). The Wald test statistic from the robust Cox model without adjustment for covariates will be using for monitoring the trial with fraction of planned households as the information fraction[1].

Table 1 Monitoring bounds with 4 interim analyses. Expected events may vary and actual stopping bound will be based on number of events observed at the time of monitoring.

Analysis	Expected number of events	Efficacy bound	Futility bound (binding)
1	19	-4.50	2.7
2	37	-3.18	0.64
3	56	-2.60	-0.52

4	74	-2.25	-1.35
5	93	-2.01	-2.01

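### The primary hazard ratio, 95% CI and p-value make no allowance for the four interim looks and binding futility bounds; the effect is small and an added sequential analysis would cover it

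*SAP*

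**What the plan says.** SAP 2.4 describes an event-driven group-sequential design: "we instead assume 90% power with 50% reduction and 4 interim analyses (for 5 total"), with "a one-sided alpha = 0.025 and a hard futility boundary". It concludes that "the design requires 93 events".

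SAP 8.1 sets the looks: "Interim monitoring will be performed on the primary outcome after approximately 20%, 40%, 60% and 80% of expected events". Table 1 there gives efficacy bounds on the Z scale of -4.50, -3.18, -2.60, -2.25 and -2.01 at 19, 37, 56, 74 and 93 events. The binding futility bounds are 2.7, 0.64, -0.52, -1.35 and -2.01. The monitoring statistic is the robust Cox Wald Z without covariates.

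SAP 7.1.1 states its objective as estimating efficacy, and then: "Efficacy will be calculated as 1 minus the hazard ratio (treatment/control) from the treatment coefficient". It displays a robust 95% CI and p-value. The reported model includes quarantine status, sex and age, and SAP 7.1 stratifies it by site and contact type. SAP 4 sets a default two-sided level of 0.05. Neither document specifies an estimate, interval or p-value that allows for the interim looks. The protocol refers to a separate Interim Monitoring Plan for redetermining sample size, which is not among the documents reviewed.

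**The concern.** The trial may stop at any of five analyses, but its result is to be reported as if there were only one. With stopping rules, the ordinary estimate is no longer median-unbiased and the ordinary 95% CI need not cover at 95%. Early stopping is also the expected route to success here: at the design effect, 86% of successful trials stop before 93 events.

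Two things are at stake. The first is the accuracy of the efficacy figure and interval that Protocol 5.1 intends for public health use. The second is consistency between the CI and the stopping rule. The final bound is -2.01, but an ordinary 95% CI excludes 1 once Z passes -1.96, and the SAP does not say which of the two governs.

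**Working it through.** **Inputs.** From SAP 2.4: HR 0.5, 90% power, one-sided alpha 0.025, 93 events, "Assuming a household attack rate of 10% in the placebo arm", and "we would need to enroll 1240 participants who are negative at baseline". From SAP 2.3: 1:1 allocation. From SAP 8.1: the Table 1 looks and bounds.

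**Assumptions.** Information is events/4, so SE(log HR) = 2/√events. Looks fall exactly at the Table 1 counts, contacts are independent, and monitoring and reporting use the same model.

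**1. Reproduce the design.**
- A fixed design (Schoenfeld) needs 4(1.960 + 1.282)²/(ln 0.5)² = 87.5, so 88 events. The plan's 93 is an inflation of 93/88 = 1.057.
- Numerical integration through the Table 1 bounds gives one-sided alpha 0.0251 (the bounds are rounded) and power 0.903 at HR 0.5.
- N = 93/((0.10 + 0.05)/2) = 1240.

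All of the plan's figures reproduce.

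**2. Where successful trials stop at HR 0.5.** Efficacy stops at looks 1 to 5 have probability 0.1%, 14.1%, 35.9%, 27.4% and 12.8%. Early efficacy stops total 77.5% of all trials, and 0.775/0.903 = 86% of successes. The observed HR needed is exp(2Z/√events): 0.127, 0.351, 0.499, 0.593 and 0.659.

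**3. Coverage and bias of the ordinary result.** The process was simulated with 2 million trials per HR. The CI is log HR ± 1.96 × 2/√events at the stopping look.

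| True HR | P(success) | Coverage, all | Coverage, successes | Median HR, all | Median HR, successes |
|---|---|---|---|---|---|
| 0.4 | 0.990 | 95.3% | 96.2% | 0.384 | 0.383 |
| 0.5 | 0.903 | 93.4% | 96.9% | 0.480 | 0.469 |
| 0.6 | 0.670 | 93.2% | 94.9% | 0.577 | 0.521 |
| 0.7 | 0.388 | 92.9% | 90.7% | 0.731 | 0.555 |

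Median efficacy follows from these:
- At HR 0.5 it is 52.0% over all trials and 53.1% among successes, against a true 50%.
- At HR 0.7 it is 44.5% among successes and 26.9% over all trials, against a true 30%.

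**4. Source of the coverage loss at HR 0.5.** Coverage is 96.4% among early efficacy stops, 61% among unsuccessful trials and 40% among early futility stops. The pieces add up: 0.903 × 96.9% + 0.097 × 61% = 93.4%. More intervals miss by understating efficacy (3.8%) than by overstating it (2.8%). With futility stopping removed, overall coverage is 94.7%.

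**5. Discrete check.** Treating each event as a binomial draw and using a Wald interval, coverage at HR 0.5 is 94.0%, the same as for a fixed 93-event design. At HR 0.6 it is 94.7% against 95.9% fixed, and at HR 0.7 it is 94.7% against 95.5% fixed.

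**6. Effect of a stage-wise correction on single results.**

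| Look, Z | Ordinary HR (95% CI) | Median-unbiased HR (stage-wise 95% CI) |
|---|---|---|
| 2, -3.50 | 0.316 (0.166-0.603) | 0.316 (0.166-0.603) |
| 3, -3.10 | 0.437 (0.259-0.737) | 0.442 (0.261-0.754) |
| 4, -2.75 | 0.528 (0.335-0.832) | 0.543 (0.341-0.875) |
| 5, -2.50 | 0.595 (0.397-0.894) | 0.620 (0.407-0.957) |
| 5, -1.98 | 0.663 (0.442-0.996) | 0.662 (0.435-1.004) |

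The last row is the inconsistent case: the bound is not crossed, yet the ordinary CI excludes 1. A final Z between -2.01 and -1.96 has probability 0.2% at HR 1, 0.5% at HR 0.5 and 1.2% at HR 0.7.

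With the correction, the all-trial median HR at a true 0.5 becomes 0.500, but the median among successes is still 0.484.

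**The case against.** The strongest reply is that the bounds already control type I error, no decision changes, and the distortion is small. At HR 0.5 the all-trial mean efficacy is 50.8% and the median 52.0%. In the discrete check the sequential design costs no coverage at that HR. All of this stands, and it makes the matter one of reporting, not of validity.

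A reader might infer more: that early efficacy stops drag coverage below 95%, that reported efficacy is generally inflated, or that a stage-wise estimate would repair a dramatic early result. The SAP's own design does not support any of these as a general statement.
- **Coverage.** At HR 0.5 early efficacy stops cover at 96.4%. Low coverage after such stops appears only with smaller effects: it is about 86% at HR 0.7, where 25% of trials stop that way.
- **Inflation.** Over all trials at HR 0.7, median efficacy is understated.
- **Repair.** A stop at look 2, where the median reported HR is 0.31 against a true 0.50, is left unchanged by the correction.

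A further fair objection is that the monitored model (no covariates) and the reported model (adjusted and stratified) differ, so stage-wise ordering does not carry over directly to the reported HR. The fix must therefore name the model. Whether the adjusted estimate should replace the Cox HR as primary is a matter of preference; adding it is enough.

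**Conclusion.** The gap is real and minor. The SAP pairs a five-analysis design with a single-look estimate, CI and p-value. Under the stated assumptions the nominal 95% interval falls short by about 1.6 to 2.1 points at HR 0.5 to 0.7, and not at all at HR 0.4. At the design effect the shortfall comes mainly from the futility side. Overstatement among successes is about 3 points of efficacy at HR 0.5 and about 14 points at HR 0.7. The possible conflict between the CI and the final bound is rare but has no rule to settle it.

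The figures rest on information proportional to events and looks at the planned counts. SAP 8.1 itself names the fraction of planned households as the information fraction. Household correlation and the difference between the monitoring and reporting models were not modelled and could shift the figures.

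**What to change.** In SAP 7.1.1:

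1. Keep the Cox HR and CI. Beside them, report a median-unbiased HR with a 95% CI and p-value from stage-wise ordering, computed from the monitoring model (robust Cox without covariates) and the bounds at the looks actually taken.
2. State that the efficacy conclusion follows the Table 1 bound and not whether the ordinary CI excludes 1.
3. State that after an early stop for efficacy the estimate may still be exaggerated, because stage-wise ordering does not remove bias conditional on stopping early.

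The cost is SAP wording, a little more analysis work, and a slightly less favourable upper limit at late looks (0.957 instead of 0.894 at a final Z of -2.50). Sample size, bounds and trial conduct do not change.
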